### Information about the medical device/s

The device used in this study is a CE marked phototherapy medical device (emitting blue light) for the treatment of skin lesions. It is a IIa class portable device, internally powered. The trade name is EmoLED (product code 9800010001), the version is v.1 and it includes a software (version 3.0) that operates the applications. The accessories provided are: safety glasses for the operator, charging adapter for the internal batteries, a shield for visual comfort and the device's case. The supplier is EMOLED S.r.l.

EmoLED is CE marked as a phototherapy device for the treatment of skin lesions. It is intended for use by medical personnel in a hospital or outpatient setting. The patients' demographic consists of individuals with skin lesions that are at least 16 years old, regardless of their ethnicity. EmoLED is conceived and designed to treat chronic and acute lesions of the skin by healthcare professionals such as doctors and nurses operating in the tissue repair field. In particular the EmoLED treatment is part of the clinical practice and the Standards of Care (SoC) provided for various types of lesions (e.g. chronic lesions or burns).

EmoLED treatment is additional to the conventional therapy consisting in the lesions cleansing and dressing with conventional or advanced medications. The recommended posology is of one treatment at every dressing change, to be performed after cleansing and before dressing.

The device is constituted by a "body" to hold, containing the battery pack, the motherboard and a touch screen, and by a rotating arm containing the optical part and the proximity sensor. The optical head has a cylindrical shape with a 50mm diameter and a 180 degrees rotation. The full rotation is prevented by mechanical means.

The front of the device contains a touch screen display through which it is possible to select the language and register as a user, manage the treatments by entering the size of the lesion and see information related to the treatment such as time and number of applications remained. The screen also displays information about the status of the device, such as the remaining charge and any error messages or warnings.

The casing is equipped with two openings on the left side containing:

- A power jack for connection to the power supply dedicated to charging the batteries;
- A micro-USB port to download data related to the use of the device collected by the way during its use. Access to these data is subject to the entry of a security password provided only to authorized personnel.

On the back of the device there is an On/Off button.

The user interface is essential and intuitive, in order to minimize the risks related to usage error. The commands are simple and like "confirm"/"cancel"/"next". The information shown on the screen is easy to understand and the meaning of all the symbols used is given in the appropriate paragraph of the User Manual.

EmoLED is a portable device, powered by rechargeable lithium-ion batteries, non-invasive and non-contact, fast in the treatment and that can be disinfected.

The interface through touch screen allows, asking 2 simple questions to the user, to set the treatment in terms of number of applications; the duration of the individual application and the delivered dose are set at the factory and are not modifiable by the user.

The device is equipped with a movable and rotating part containing the Optical Head, from which the incoherent light beam generated by 6 LEDS that emit in the blue range (between 410 and 435 nm, Optical Power Density 120 mW/cm^2) comes out, in order to facilitate the treatment of the lesions of interest. The emission of light radiation is subject to the correct positioning of the device towards the lesion: target treatment distance 40 ± 10 mm. The positioning is controlled by an electronic card containing a distance sensor. The use of the device is excluded when charging the batteries.

Accessories supplied with the device:

- Power supply;
- Screen for visual comfort;
- UV filter glasses.

The visual comfort screen is located just behind the light beam area and provides physical protection against emitted components that can prove troublesome when reflected. The charger is a 24 V power supply with an integrated cable to connect the device and a separable cable to connect to the network. On request, protective glasses with UV filtration and Optical Density (OD) of 4+ up to 400 nm and at least 2+ between 400 and 460 nm are provided. These PPE are recommended for both the operator and for all people within a radius of 1 meter from the source of light. The glasses available are the 450#53 model of the NOIR Laser Company.

The device is supplied by manufacturer with certified quality management system, traceability is guaranteed by the manufacturer's system which, through the serial number, is able to know both where the device in question is located, and the details of the internal components of the device.

The EmoLED device is very simple and intuitive in its use, the user manual illustrates the proper use. Moreover, the device operators will attend a manufacturer's training session in which the proper use of the device is explained and a demonstration test is performed. Emoled staff is always available for any question, request and for assistance.

The blue light emitted by the device interacts with the endogenous chromophores of the skin triggering reactions that lead to the activation of certain cellular pathways. In particular, the wavelength emitted by the device is absorbed by Protoporphyrin IX present in Cytochrome C, an essential protein for cellular respiration at the mitochondrial level. The energy absorbed is used by the cell to increase the production of ATP, a fundamental molecule for all the processes involved in tissue repair. In addition, blue light is able to stimulate the production of ROS (Reactive Oxygen Species) through the excitation of flavins and flavoproteines. Nowadays, multiple evidence has been produced about how ROS can be considered signal transducers of numerous cellular pathways. This consideration validates the evidence that ROS (at physiological concentrations) are crucial for multiple cellular functions such as differentiation, proliferation, migration and contraction.

Therefore, it follows from those considerations that blue light can promote and restore the correct course of tissue repair in wound that are considered "difficult" or chronic.

### **Literature review and rationale of the clinical investigation**

Proper wound management and dressing after surgery, trauma or disease is an important part of the healing process, not only to prevent infections or other complications, but also to accelerate wound healing with as little scarring as possible.

Wound healing is a complex and dynamic biological process that includes a series of organized phases, including coagulation, inflammation, matrix deposition, angiogenesis, proliferation, cell remodeling and wound contraction (2, 3). So that each step of the process is completed, complex interactions between various biological factors need to occur, such as growth factors and proteinases, matrix components and various cell types, such as platelets, macrophages, fibroblasts and endothelial cells (4). The interaction of these processes as a whole determines the restoration of tissue integrity and functional healing (5). Although much has been done towards the complete understanding of the processes that regulate this important

biological function, there are many aspects that still need to be clarified. At the same time, if it is true, on the one hand, that technological advances have led to the creation of increasingly sophisticated medications, it is equally true, on the other hand, that there is a need to find new methods to further improve the healing process, regardless of the event causing the skin injury, reducing the pain and discomfort associated with the medication itself, possibly shortening the time needed to recovery, with relative reduction of related costs.

Evaluating the scenario of the patient suffering from diabetic pathology and focusing only on one of its complications, our country has a unique organization for the management of the Diabetic Foot, based on 176 dedicated Units divided into 3 levels of care:

- 1° Level: territory general practitioner: screening and treatment of uncomplicated injury;
- 2° level: diabetic foot care center: prevention, diagnosis and treatment of non-ischemic ulcers (complicated lesion);
- 3° level: operating unit specifically dedicated to diabetic foot treatment (critical injury and/or recurrence).

Despite a dedicated organization, in 55-66% of cases the duration of diabetic foot ulcers (DFU) is not known, or the diagnosis is delayed by more than 3 weeks from the appearance of the ulcer. The delayed sending of acute DFUs carries a high risk of amputation (about 50% of total amputations affect diabetic patients). Guidelines and protocols are often not recognized and followed: 30-40% of general practitioners consider the management of DFUs unclear for the absence of Standards of Care and specific paths.

The availability of podological clinics in the Anti-diabetes Centers in Italy is still not homogenous and most of the Centers does not present the professional figure of the podiatrist within the multidisciplinary team.

This clinical trial will be a prospective, single-center, randomized controlled parallel group, superiority study with the commercial objective of evaluating the clinical efficacy of a battery-powered portable device that uses blue LEDs. The study aims, over the planned observation weeks, to clinically compare two groups of patients with neuro-ischemic foot lesions in patients with type I or II diabetes. The aim is to determine any differences in outcome between the two groups that are considered and whether the therapy of the treatment group is a valid alternative to current therapy in terms of percentage of patients healed, speed of healing, quality of life and economic impact.

Group 1, the control group, will follow the standard treatment provided by the facility protocol with wound cleaning and adequate dressing. Group 2, the treated group, will follow the standard treatment provided by the hospital protocol with wound cleaning and adequate dressing, adding the treatment with the Emoled device, which is set between the cleansing and the application of the dressing. This treatment consists in irradiating with the blue light emitted by the device, for two minutes, each circular area with a diameter of 5 cm of the lesion, twice a week for twenty weeks.

The measurement of the difference in efficacy of the device between the two groups will be evaluated in terms of percentage of patients healed, intended as a 100% re-epithelialization of the lesion. Therefore, this clinical trial aims to investigate whether the group of patients undergoing standard therapy with, in addition, the Emoled treatment reaches a percentage of healed patients and / or a healing speed higher than the control group. If confirmed, this result would imply significant gains in terms of reduction of outpatient visits / home visits and therefore also in terms of reduction of public health costs, thus also increasing the quality of life of patients suffering from neuro-ischemic diabetic foot ulcer.

The population subject of this trial is widely representative of the target population and the center involved is a structure of excellence in the treatment of diabetic foot lesions under study.

The EmoLED device, CE marked (certificate n. G1 18 02 99242 002), has been used in its prototype version in three different clinical studies. The first two studies analyzed the efficacy of EmoLED on (acute) surgical lesions, the third, on the basis of some spontaneous observations from professionals in the sector, evaluated the efficacy of continuous therapy on chronic lesions.

A fourth study, currently under way, aims to assess, in addition to clinical efficacy and safety, also the impact of treatment with Emoled device on the quality of life of patients and socio-economic aspects related to chronic leg ulcers.

The clinical safety of the device was therefore evaluated in previous studies which, having a comparison, demonstrated the superiority of treatment with EmoLED compared to other advanced therapies.

In the context of this study, neuro-ischemic foot injuries (grade IC or IIC according to the University of Texas Wound Classification) will be considered in patients with type I or II diabetes in "mixed" Hospital - Territory treatment. The details of the application of the treatment will be explained later; in any case, however, the treatment with EmoLED consists in irradiating the lesion for two minutes with the light emitted by the device.

This treatment does not interfere with other systemic therapies that may be in place, nor does involve any additional risk compared to standard treatment; the potential benefit is imputable not only to a reduced healing time and a greater probability of healing, but also to the reduction of pain and the improvement of the quality of life, with the consequent indirect benefits.

#### *Principle of operation of the EmoLED medical device to help wound healing*

The EmoLED device is a medical device for the healing of wounds, CE marked, whose operation is based on LED sources operating in the blue range.

The choice of blue light was made on the basis of the absorption spectrum of the target chromophore - the Protoporphyrin IX present in Cytochrome C; actually, the emission range of EmoLED medical device is preferentially absorbed by this chromophore as it coincides with its maximum peak absorption in the visible light spectrum.

As for the use of light in medicine, the scientific literature is rich in data and evidence on its use for the treatment of acne (6) and psoriasis (7) and its effectiveness in accelerating the process of healing of an induced wound on animal models (8-10).

When considering the absorption coefficients of the skin chromophores in the visible light range, we note that Cytochrome C has the peak of maximum absorption in the range of blue, around 410 nm for both the reduced and oxidized form.

A way through which EmoLED can act in tissue repair is the chain of mitochondrial electronic transport. EmoLED in particular can act on the last two complexes that contain Cytochrome C, that is sensitive to visible light in the range of emission of the device.

The resulting effect is the strengthening of this process and the increase in ATP production, related to the development of a proton gradient dependent on the electron transport chain.

The increase of ATP production determines an increment of the available energy for the cell that can intensify its metabolic activity, a necessary process during the repair of an injury that involves activation of different cell types and an additional energy effort for the organism.

Other important effects of EmoLED device are mediated by the action of ROS, signal transducers of numerous cellular pathways that are involved in tissue repair. A moderate increase in ROS stimulates the production of pro-inflammatory agents (13-15).

Furthermore, through the action on the T lymphocytes present in the wound bed, ROS are able to promote the phenotypic transition of macrophages from M1 (pro-inflammatory) to M2 (pro-healing) (16,17). This combination of effects suggests a positive action on the inflammatory stasis that characterizes some types of "non-healing" wounds: an increase in inflammation such as to induce the body to a consistent response and the consequent stimulation for the following phases.

Through the production of HIF-1 $\alpha$  (Hypoxia-inducible factor 1-alpha) and the consequent release of proangiogenic factors and induction of eNOS (endothelial Nitric Oxide Synthase) ROS also play a role in promoting angiogenesis (18,19) and therefore in the increase of the nutrient and oxygen supply in the wound bed, of great importance in the proliferation phase.

The device has been designed and set to deliver a power density of about 7 J/cm^2 in an acceptable treatment time for both doctor and patient: 60 seconds for each circular area of 5 cm diameter that needs to be treated.

The choice of the duration of the treatment was also made on the basis of what is stated in literature on thermal damage: the treatment induces a temperature between 45 and 50 °C in the treated area, ideal condition to stimulate the reversible and physiological phenomena that we want to induce. On (11) page 78 there is an attached table showing the physiological phenomena induced by temperature:

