### **Medical-surgical procedures and study follow up**

Standard treatment, according to the most recent version of the IWGDF guidelines (IWGDF – International Working Group on Diabetic Foot < <https://iwgdfguidelines.org/wp-content/uploads/2019/05/IWGDF-Guidelines-2019.pdf> > ), includes debridement of the lesion, offloading with a device up to the calf, non-

removable (except for contraindications), dressing of the wound with advanced dressings in use at the trial center and at the home care according to SoC, to be renewed biweekly.

For the purposes of the study, in order to standardize the standard treatment as much as possible, all patients, except for contraindications, will adopt the same brace, made irremovable [Optima Diab, Molliter, Civitanova Marche (23-24)]

The treatment with EmoLED, in addition to the standard treatment, will be performed twice a week in correspondence with the dressing change of the lesion by the Home Care Nursing Service, blinded to the doctors of the specialist center, for twenty consecutive weeks, for a total of 40 treatments.

Treatment with the EmoLED device consists of irradiating each area of 5 cm in diameter of the lesion for 2 minutes; if the lesion is wider than 5 cm in diameter, the applications will be repeated to cover the entire area of interest. EmoLED treatment is additional to standard patient therapy.

During the twenty weeks of treatment with the EmoLED device and until healing, treatments with other types of phototherapies (including photodynamic therapies), topical negative pressure therapy, or other therapeutic interventions in addition to standard therapy will not be allowed.

In the event of clinical signs of infection of the wound, in the case of mild, moderate or severe infection according to I.D.S.A. (25), the lesion will be treated with antiseptic medication and, if deemed necessary by the investigator, with systemic anti-infective therapy, identified by medical personnel. The onset of infection will be reported in the appropriate section of the Data Collection Form and eventually reported to the promoter in case of serious infection (Serious Adverse Event).

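### The protocol's only stated light dose, about 7 J/cm² in 60 seconds per 5 cm area, is half of what the prescribed two minutes delivers at the stated irradiance

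*Protocol*

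**What the plan says.** Three parts of the Protocol bear on the light exposure.

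- **Device description** (Information about the medical device/s). The emission is given as "between 410 and 435 nm, Optical Power Density 120 mW/cm"², that is, 120 mW per square centimetre. The touch screen's function is described as follows: "to set the treatment in terms of number of applications; the duration of the individual application and the delivered dose are set at the factory". Operators cannot alter either setting.
- **Dose and duration rationale** (Principle of operation of the EmoLED medical device to help wound healing). The device is "designed and set to deliver a power density of about 7 J/cm"², in a treatment time of "60 seconds for each circular area of 5 cm diameter that needs to be treated". The section bases this duration on literature about thermal damage, quoting 45 to 50 °C in the treated area, and on a model linking optical power, treatment time and final temperature.
- **Trial regimen.** The Literature review and rationale section has the treated group irradiated "for two minutes, each circular area with a diameter of 5 cm of the lesion, twice a week for twenty weeks", and later repeats that "the treatment with EmoLED consists in irradiating the lesion for two minutes with the light emitted by the device". The Medical-surgical procedures and study follow up section agrees: "Treatment with the EmoLED device consists of irradiating each area of 5 cm in diameter of the lesion for 2 minutes". It adds that "if the lesion is wider than 5 cm in diameter, the applications will be repeated to cover the entire area of interest".

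No other section gives a dose in J/cm².

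**The concern.** The light dose is the intervention being tested. The regimen is two minutes wherever it is prescribed, yet the one section that states a dose and justifies the treatment time works with 60 seconds for the same 5 cm circle. Nothing explains the doubling.

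Three things depend on it.

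- **Delivery.** Application length and dose are factory-set, and the operator works in numbers of applications. If one application lasts 60 seconds, the protocol does not tell the home-care operator that a lesion of 5 cm or less needs two.
- **Adherence.** The section on clinical evaluation plan deviations treats a change in the timing or method of device treatment as a major deviation. With two exposure times on the page, the reference for judging that is unclear.
- **Later use.** The Sample number section presents the trial as a proof of concept to inform later studies. A reader who takes the dose from the principle-of-operation section would carry forward half the prescribed exposure.

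The duration rationale is also affected: a thermal argument that depends on exposure time does not automatically extend to twice that time.

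**Working it through.** **Inputs, all from the Protocol**

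| Quantity | Value | Section |
|---|---|---|
| Irradiance | 120 mW/cm² = 0.120 W/cm² | Information about the medical device/s |
| Stated dose | about 7 J/cm² | Principle of operation |
| Time tied to that dose | 60 s per 5 cm circle | Principle of operation |
| Prescribed time | 120 s per 5 cm circle | Literature review and rationale; Medical-surgical procedures |
| Number of treatments | 40 | Medical-surgical procedures |

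**Formula.** Energy density (J/cm²) = irradiance (W/cm²) × time (s).

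**Step 1: reproduce the stated dose.** 0.120 × 60 = 7.2 J/cm². This is (7.2 − 7)/7 = 2.9% above 7, so irradiance, 60 seconds and the stated dose fit together.

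**Step 2: the prescribed exposure.** 0.120 × 120 = 14.4 J/cm². The ratio to step 1 is 14.4/7.2 = 2.0; against the stated 7 it is 14.4/7 = 2.06.

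**Step 3: can rounding or another irradiance explain it?** To deliver 7 J/cm² in 120 s the irradiance would have to be 7/120 = 0.0583 W/cm², or 58 mW/cm², about half the stated 120. If the approximate 7 is read as 6.5 to 7.5 J/cm² (an assumption), the time at 120 mW/cm² is 6.5/0.120 = 54 s to 7.5/0.120 = 63 s. Two minutes lies far outside that range.

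**Step 4: over the course.** For an area treated at all 40 sessions, 40 × 7.2 = 288 J/cm² against 40 × 14.4 = 576 J/cm².

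**Step 5: is the factor of two explained elsewhere?** The only other exposure times in the Protocol are 30 seconds, in the first acute-wound study and in the animal work. Neither comes with a dose, and neither supports two minutes. Two 60-second applications on one area would give 2 × 7.2 = 14.4 J/cm² and resolve everything, but this is not stated. The procedures section mentions repeats only as a way to cover a lesion wider than 5 cm.

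**Unit.** The principle-of-operation section calls the J/cm² figure a power density. J/cm² is energy per area; the device description uses the term correctly, for mW/cm².

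**The case against.** The strongest reply is that the regimen itself is consistent. Every section that prescribes treatment in this trial says two minutes, and the 60 seconds appears only in a description of how the device works. Since the device is set by number of applications, two applications per area is a natural reading, and the delivered dose can be derived from irradiance and time. Operators receive manufacturer training with a demonstration and have a user manual, and the screen shows remaining time and applications. The device may therefore assign the right number of applications itself. On this view one explanatory sentence is missing and nobody is shown to be mis-dosed.

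Much of this stands. The operative instruction is uniform, mis-dosing is not shown, and the operator gap is conditional on an application lasting 60 seconds, which the Protocol does not say.

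It does not remove the discrepancy. The principle-of-operation section describes how the device is set, carries the only J/cm² figure, and supplies the rationale for treatment time. The two-application reading is written nowhere. Training may fill the gap in practice, but the protocol is the document against which delivery will be judged.

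It can also be said that the software and temperature points are separate matters. They add nothing to the factor of two. They belong with the correction only because the software operates the applications and because the temperature figures depend on exposure time.

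**Conclusion.** The concern holds. By the Protocol's own figures, the prescribed two minutes delivers 14.4 J/cm² per 5 cm area per session, against a stated dose of about 7 J/cm² (7.2 by calculation). That is a factor of two, with no explanation in the document. The stated dose fits 60 seconds and cannot be made to fit 120 seconds by rounding.

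This rests on the stated 120 mW/cm² applying throughout the exposure and on the two minutes being spent on a single 5 cm area, as the rationale and procedures sections say.

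It should be fixed, but its reach is limited. No harm can be inferred from the document, and randomisation, endpoint and analysis are untouched. Nothing here shows which exposure or dose is the intended one.

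**What to change.** Reconcile the device description, the rationale, the principle-of-operation section and the procedures section so that they state:

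1. one exposure time per 5 cm area;
2. how many applications make up that exposure, including for a lesion of 5 cm or less;
3. the resulting J/cm², labelled as energy density.

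Confirm that the factory setting of the trial devices matches, for the software version actually in use. The device description names version 3.0, while the risk analysis cited under the conditions where no report is required names version 2.1.

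State which exposure time the temperature figures refer to: 45 to 50 °C in the principle-of-operation section, and never above 40 °C in the section on human acute-wound observations and ulcer cases.

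The choice of values belongs to the sponsor and investigators. The cost is a wording amendment and a check of the device setting, best done before the first patient is treated if recruitment has not begun. No design change is needed.
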